|                                |  |
|--------------------------------|--|
| Title:                  | Trends in intraoperative transfusion thresholds and association with post-operative outcomes: A Report From the Multicenter Perioperative Outcomes Group (MPOG)  |
| Principal Investigator: | [name] [name], MPH   |
| Co-Investigators:       | [name] MB BCh, FRCA
[name] BM BS, FRCA
[name] PhD
[name] MS
[name] MD, MMM
[name] MD, MBA
[name] MD
[name] MB ChB, MRCP, FRCA
And other interested MPOG investigators  |
| Type of Study:          | Retrospective observational – descriptive study  |
| IRB Number / Status:    | University of Michigan: HUM00052066 / Accepted   |
| Aims:                   | 
 
1) To investigate the trend in measured hemoglobin/hematocrit and subsequent transfusion in a US academic general surgery population
 
2) To investigate factors associated with transfusion (particularly institution, temporal trend, surgery type and presence of cardiac disease)
 
3) To investigate the relationship between transfusion and post-operative mortality, AKI or myocardial injury.
 
 |
| Patients/Participants:  | 
Inclusion: 18yrs or older. Undergoing orthopedic, general, vascular, gynecologic, urologic, ENT or thoracic surgery. Inpatient stay. At participating MPOG institution.
 
Exclusion: Transfusion >3u PRBCs during a single case, Outpatient Surgery, Cardiac Surgery or ASA 5 or 6 Classification.
  |

|  |   |
|--|---|
| 
Proposed statistical test/analysis:
 | 
For our primary and second outcomes, the trend of median pre-transfusion hemoglobin by quarter will be assessed for any change over time by testing whether the slope is significantly different from 0 using a bivariate linear regression model with the dependent variable of median pre-transfusion hemoglobin. If the slope is different than 0, then a Joinpoint analysis will be conducted to determine if there are any inflection points in the trend and reported accordingly. ANOVA will be used to determine if the proportion of cases receiving PRBC significantly changes through the study period. In addition mixed-effects logistic regression models will be developed to determine independent predictors of secondary outcomes 4 and 5 as outlines in the study protocol.
 |
| 
Resources:
                          | 
Perioperative records query from MPOG-participating institutions, performed with support of MPOG Coordinating center.
  |

## Introduction

Packed red blood cell transfusion can be lifesaving in the treatment of bleeding and in the US alone, 13.6 million units of blood are collected each year. However transfusion is associated with major morbidity and mortality, therefore, it is critical to identify those for whom this therapy will provide the most benefit.

Older, observational data from patient populations who refuse transfusions of red blood cells demonstrates increasing morbidity and mortality as hemoglobin concentrations fall below 7.1-8 g/dL, with significant mortality accrued below 5 g/dL. A succession of large, prospective randomized controlled trials have subsequently been performed to compare restrictive transfusion (with varying hemoglobin thresholds between 7-8 g/dL) with liberal transfusion (using thresholds of 9-10 g/dL) practice. Meta-analyses of these studies have not shown differences in mortality between groups in orthopedic trauma, cardiovascular surgery, or unselected hospitalized populations; recommendations regarding the utilization of restrictive transfusion practice have subsequently been incorporated into professional society guidelines worldwide. Some controversy remains in patients with ischemic cardiac disease.

Surveys of blood banks reveal that transfusions of packed red blood cells have declined overall. From Europe, a large prospective observational trial revealed pre-transfusion hemoglobin of 8.1 g/dL prior to intraoperative transfusion, however noted that in 41% of cases providers gave more than 1 unit of packed red blood cells irrespective of the starting hemoglobin. This study did not examine patients in whom transfusion was not performed and were unable to comment on patient outcomes.

It is not yet clear how the results of this increasing body of work favoring restrictive transfusion practice has translated into intraoperative clinical practice within the United States. Therefore, we seek to perform a retrospective observational study to evaluate trends in transfusion practices and to assess changes in outcome in patients undergoing major surgery within centers in the United States.

We hypothesized that: 1) We would observe a reduction in pre-transfusion intraoperative hemoglobin, as a proxy for transfusion trigger, and reduction in nadir hemoglobin in cases where intraoperative transfusion was not performed. 2) A diminishing number of intraoperative transfusions would be observed, overall and at each hemoglobin value. 3) There would be a reduction in the nadir postoperative hemoglobin. 4) That any observed trends would be modulated by year, surgery type, institution and the presence of coronary artery disease. 5) That in the presence of a change in transfusion practice, we would not observe a change in mortality, post-operative myocardial injury or acute kidney injury.

## Methods:

The MPOG Consortium assembles a database of perioperative information of patients undergoing anesthetic care at institutions across the US and the Netherlands. Data is assembled from electronic health record systems (including anesthesia specific systems), administrative, laboratory and outcome data sources. Full details of the functioning of the MPOG Consortium are described elsewhere. IRB approval for this study is provided by University of Michigan Institutional Review Board (HUM00052066). Sites participating in the MPOG collaborative obtain local IRB approval to assemble, organize and transmit this dataset. In keeping with the normal operating procedure of the MPOG collaborative the study protocol was presented to and approved by the MPOG Perioperative Clinical Research Committee (PCRC) on October 9th 2017. It was finalized on Feb 2nd 2018, prior to data extraction or analysis. A completed STROBE checklist for this study is attached to this manuscript (Appendix 1).

Sites will be included if they participated in the MPOG collaborative and data, including perioperative labs, and hospital and professional billing data were consistently available for the period between January 1, 2012 and July 1, 2017. We anticipate including data from 8 participating US sites: Cleveland Clinic, University of Colorado, University of Michigan, University of Oklahoma, University of Tennessee, University of Vermont, University of Virginia and Vanderbilt University.

Subjects will be included in the study if they were 18 years or older at time of surgery, underwent an orthopedic, general, transplant, vascular, gynecologic, urologic, neurosurgery, plastic, ENT or thoracic procedure with an associated inpatient stay. Subjects will be excluded if they underwent transfusion of greater than 3 units of packed red blood cells during the intraoperative period, underwent outpatient surgery, cardiac surgery, obstetric surgery, any procedure involving CPB or were assessed as having an ASA physical status classification of 5 or 6. Case groupings will be performed based on Anesthesia CPT Codes (see Appendix 2).

The primary outcomes of this study are: the change in the pre-transfusion hemoglobin (ie transfusion threshold) and the nadir hemoglobin not-followed with an intraoperative transfusion over the course of the study period. The secondary outcomes of this study are: proportions of cases receiving a packed red blood cell transfusion throughout the study period (including stratification by prior laboratory measurements); the number of units of packed red blood cells transfused during the intraoperative period; the nadir postoperative hemoglobin (lowest value measured 0 – 72 hrs after the completion of intraoperative anesthesia care), the relationship between patient, surgical and institutional factors and the occurrence of transfusion and determination of the subsequent impact of any transfusion trends on blood product utilization; the relationship between in hospital mortality, post-operative myocardial injury, acute kidney injury and the pre-transfusion hemoglobin (for transfused cases – definition below) and lowest (for non-transfused cases) intraoperative hemoglobin.

In this study, we define coronary artery disease based on the present of a discharge ICD9/10 as listed in Appendix 3. Determination of AKI was based on the KIDIGO laboratory based definition AKI (Cr rise of 0.3 mg/dL rise within 48hrs of anesthesia end time or rise by more than 50% in 7 days). We will use intraoperative hemoglobin values documented, regardless of method of measurement. We preferentially use hemoglobin measures over hematocrit if these are documented simultaneously. If only a hematocrit is present at the time of lab measurement, we will perform an estimated conversion to hemoglobin, by dividing by 3. For blood transfusions documented exclusively in volume based units, we will convert this to units by assuming that any blood volume transfused greater than or equal to 250ml and less than or equal to 450 ml in one charting increment corresponds to one unit of blood.

For those transfused, the hemoglobin analyzed will be the value immediately prior to the transfusion of the case. In the cases with multiple transfusions, it will be the highest of the identified pre-transfusion hemoglobin measures across each of the transfusions. We will define immediately prior to transfusion as the lab value drawn closest to transfusion within a 30-minute pre-transfusion window. If this proves too restrictive and more than 30% of pre-transfusion lab values will be excluded, the window will be liberalized to 45 minutes. The hemoglobin measurement identified is referred to as the “pre-transfusion hemoglobin” throughout this document. For those who were not transfused, the nadir hemoglobin will be the lowest value of the case.

The covariates to be included in all models (discussed below) are surgical specialty (defined based on anesthesia CPT Code assigned to the case), age, BMI, sex, presence of coronary artery disease (defined by ICD 9/10 codes), Elixhauser comorbidities, quarter of the study period, and nadir hemoglobin. The unit of measure for time used in trend analysis will be by quarter. The use of autologous blood will not be considered in this analysis. Patients who receive exclusively cell saver blood (and no PRBCs) will be considered not to be transfused for the purposes of the analysis.

We will describe the proportion of cases with a non-red blood cell blood product administered and the frequency of use of measures of coagulation (PT/INR, PTT, PLTs etc) as documented in the anesthesia record and the use of “cell saver” blood. Additionally, we will perform a survey of participating institutions to determine if formal blood transfusion protocols or blood transfusion management efforts, pre-operative preparation strategies were routinely used and which point of care coagulation tests were in place at the time the studied cases occurred.

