**Secondary Outcome 2: The number of units of packed red blood cells transfused during the intraoperative period.**

The number of units of pRBC transfused during the intraoperative period will be analyzed similar to Primary Outcome 1.

To determine independent predictors of the number of units of pRBC transfused during a case, two mixed effects linear regression models will be constructed with the independent covariates listed in the methods and the dependent variable of number of units of packed red blood cells transfused. The first model will contain the mixed effect of institution, and the second model will contain the hierarchical mixed effects of primary attending nested within institution.

**Secondary Outcome 3: The nadir postoperative hemoglobin (lowest value measured 0 – 72 hrs after the completion of intraoperative anesthesia care)**

The lowest postop hemoglobin will be examined for a trend over time for all cases using a Joinpoint analysis as for previous outcomes. The lowest postop hemoglobin will be compared at each time point between those with and without an intraoperative transfusion using a Student's t test or Mann-Whitney U test, as appropriate.

**Secondary Outcome 4: The relationship between patient, surgical and institutional factors and the occurrence of transfusion and determination of the subsequent impact of any transfusion trends on blood product utilization.**

Two mixed-effects logistic regression models will be used to determine if surgery type, year, and cardiac disease are independent predictors of intraoperative transfusion. The outcome of intraoperative transfusion will be defined as any PRBC use between Anesthesia Start and

Anesthesia End. The first model will contain the mixed effect of institution, and the second model will contain the hierarchical mixed effects of primary attending nested within institution. Independent variables to be included in the model are: Age, Sex, Elixhauser co-morbidities (as numeric and also CAD y/n, heart failure y/n, cancer y/n), WHO BMI classifications, ASA Status, Pre-op Hb, lowest Intra-op Hb for cases without intraop transfusion or the pre-transfusion hemoglobin, Pre-op Plts (abnormal y/n), Pre-op Creatinine (abnormal y/n), Abnormal coags (y/n – PT, PTT or INR), Surgical Specialty, EBL, Cell saver (Scavenged) blood use (y/n), Emergent Surgery, Use of anti-fibrinolytics (Aminocaproic Acid, Tranexamic Acid, Aprotinin) – y/n, and surgical Case Duration.

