To determine if transfusion practice changed over time, a multivariable linear regression model will be constructed as above, with the outcome of intraoperative hemoglobin (lowest throughout the case for those who were not transfused and prior to transfusion as defined above for those who received an intraop transfusion). The covariate of intraoperative transfusion y/n will be added to the list specified above. Model-based least square means with standard error will be reported and compared between those who were transfused and those who were not with a Student's t test. These means are the adjusted marginal mean of the outcome for the population, which we will consider a proxy for transfusion threshold. A one-way t-test will be used to test if the model-based mean hemoglobin for those who were transfused changed over time.

An observed vs. expected analysis will be conducted for the occurrence of transfusion, comparing practice patterns between the first and last time periods (quarters/half-years/years as appropriate) using a Chi-squared or Fisher's Exact test.

**Secondary Outcome 5: The relationship between in hospital mortality, post-operative myocardial injury, acute kidney injury and intraoperative hemoglobin concentration (with and without transfusion).**

Due to the small sample size expected for in-hospital mortality and post-operative myocardial infarction, the outcome for this analysis will be a composite variable of post-operative morbidity and mortality. Multiple mixed-effects logistic regression models will be used to determine if perioperative hemoglobin is an independent predictor of post-operative morbidity and mortality in ranges which are typically considered consistent with restrictive transfusion. In one model the lowest intraoperative hemoglobin will be considered as a continuous variable, for modelling outcome, in another, we will compare lowest intraoperative hemoglobin ranges of <6 g/dL, 6-7 g/dL, 7-8 g/dL, 8-9 g/dL, 9-10 g/dL, > 10 g/dL. Due to sample size constraints, we may have to redefine these boundaries. We will further analyze this to include the mixed effect of institution, and the second model will contain the hierarchical mixed effects of primary attending nested within institution. All models will include transfusion as a binary variable.

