## Sample Size:

Based on a rough approximation of the inclusion criteria using DataDirect, we found around 113,000 cases with intraoperative Hemoglobin/Hematocrit values, which should provide sufficient power for all planned analyses.

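### No rule covers repeat operations in one admission, so Secondary Outcome 5 can count one death (and possibly one AKI) on two rows treated as independent

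*Protocol*

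**What the plan says.** **Unit.** The Sample Size section counts cases, not patients or admissions: "we found around 113,000 cases with intraoperative Hemoglobin/Hematocrit values, which should provide sufficient power for all planned analyses". Secondary Outcome 3 also runs on cases: "The lowest postop hemoglobin will be examined for a trend over time for all cases". Eligibility in Methods is worded by subject and requires a "procedure with an associated inpatient stay". The exclusions begin "Subjects will be excluded if they underwent transfusion of greater than 3 units of packed red blood cells during the intraoperative period" and go on to outpatient, cardiac, obstetric and bypass procedures and ASA 5 or 6. Repeat operations are not among them, and neither the summary table nor Methods has a first-case or one-case-per-admission rule.

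**Windows.** Methods defines "the nadir postoperative hemoglobin (lowest value measured 0 – 72 hrs after the completion of intraoperative anesthesia care". AKI is a creatinine "rise within 48hrs of anesthesia end time or rise by more than 50% in 7 days". Mortality is in-hospital. No window is given for myocardial injury, so nothing is claimed about it here.

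**Models.** In Secondary Outcome 5, "the outcome for this analysis will be a composite variable of post-operative morbidity and mortality". Its exposures are the case's own intraoperative hemoglobin and a yes/no transfusion term. The random effects, there and under Statistical Analysis, are institution, and attending within institution. None is for patient or admission.

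**The concern.** Take a patient operated on day 0 who returns to theatre on day 2, with both cases eligible and both with an intraoperative hemoglobin.

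- If the patient dies before discharge, the death is an event on both rows of the Secondary Outcome 5 models. Each row has its own hemoglobin and transfusion status.
- A creatinine rise after the second operation can meet the AKI definition for both cases, because the 7-day periods overlap.
- A hemoglobin value from the second operation can become the first case's 72 h nadir, which Secondary Outcome 3 then compares by the first case's transfusion status.

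Return to theatre is plausibly related to bleeding, transfusion and death, so the duplicated rows are unlikely to be a random sample. At stake is Aim 3, the relation of transfusion and hemoglobin to outcome. Some events would be counted twice, and the confidence intervals would assume an independence between rows that does not hold.

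**Working it through.** **Figure to reproduce.** The 113,000 is a database count. The protocol gives no event rate, effect size or return-to-theatre rate, so there is no calculation to reproduce and the size can only be illustrated.

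**Inputs.** N = 113,000 cases, from Sample Size. The rest are assumptions:
- r, the share of admissions with exactly two eligible cases: 2% to 10%.
- p1, in-hospital mortality with one case: 1%.
- p2, in-hospital mortality with two cases: 1% to 8%.

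**Formulas.**
- Admissions A = N/(1 + r).
- Deaths = A[(1 − r)p1 + r·p2].
- Death rows when counted by case = A[(1 − r)p1 + 2r·p2].
- Excess = r·p2 / [(1 − r)p1 + r·p2].

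| r | p2 | Admissions | Deaths | Death rows | Excess |
|---|---|---|---|---|---|
| 2% | 1% | 110,784 | 1,108 | 1,130 | 2.0% |
| 2% | 5% | 110,784 | 1,196 | 1,307 | 9.3% |
| 5% | 3% | 107,619 | 1,184 | 1,345 | 13.6% |
| 5% | 5% | 107,619 | 1,291 | 1,560 | 20.8% |
| 10% | 5% | 102,727 | 1,438 | 1,952 | 35.7% |

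With p2 = 8% the figures per 100 admissions are:
- r = 5%: deaths 0.95 + 0.40 = 1.35; death rows 0.95 + 0.80 = 1.75; excess 0.40/1.35 = 29.6%.
- r = 8%: deaths 0.92 + 0.64 = 1.56; death rows 0.92 + 1.28 = 2.20; excess 0.64/1.56 = 41.0%.

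The excess depends only on r and on the ratio p2/p1. When the two mortalities are equal it is simply r. The upper end needs both frequent returns and a mortality eight times higher in re-operated patients.

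**Secondary Outcome 3.** If a share q of cases has a return within 72 h and the second operation lowers the recorded nadir by a further d, the mean shifts down by q·d. With assumed q = 1% to 5% and d = 0.5 to 2 g/dL, that is 0.01 × 0.5 = 0.005 to 0.05 × 2 = 0.10 g/dL.

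**Cases lost with one case per admission.** r/(1 + r) = 2.0% at r = 2%, 4.8% at r = 5%, 7.4% at r = 8% and 9.1% at r = 10%.

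**The case against.** **It is an omission that a statistical analysis plan could fill.** Index-case rules and de-duplication often sit there, and that document is not at hand. But this protocol itself fixes the windows, the exclusions and the clustering terms. Followed as they stand, they duplicate events.

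**A reader might infer that the protocol admits every eligible operation.** It does not say so. Eligibility speaks of subjects and of a procedure in the singular, so one case per patient may be intended. The analysis sections speak of cases, and no sentence says which case would be kept. The supported statement is that the unit is not fixed.

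**A reader might infer that a death or AKI after re-operation is wrongly charged to the first case.** That goes too far. Such an event is a true postoperative outcome of the first case and may follow from it. For death, what stands is the repeated count and the unmodelled dependence between rows.

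**A reader might take the over-count of deaths as the bias in the results.** It is not. No per-case death rate is planned. Secondary Outcome 5 models a composite because few deaths and infarctions are expected, and neither the direction nor the size of any change in an odds ratio has been calculated.

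**Secondary Outcome 3 is descriptive.** This stands. It claims no effect of the index operation, the mean shift is small, and a stable return rate would not create a time trend.

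**Conclusion.** The concern holds in limited form. The protocol analyses cases, attaches outcomes to each case and models clustering only by institution and attending. Two eligible cases in one admission therefore yield duplicated events and falsely independent rows in Secondary Outcome 5, and can carry hemoglobin values from one operation into another's nadir in Secondary Outcome 3.

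The size is undetermined. The 2% to 41% range rests wholly on assumed return-to-theatre and mortality rates and describes death counts only. The 0.005 to 0.10 g/dL shift is equally assumption-based. The documents do not support a stated bias in the hemoglobin or transfusion odds ratios, or a stated degree of narrowing of their intervals.

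The two primary outcomes use intraoperative values, so the postoperative windows do not touch them. The point deserves correction before analysis but does not threaten the study's main result.

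**What to change.** 1. State the unit of analysis in Methods, and say how a second operation in the same admission is treated.
2. For Secondary Outcomes 3 and 5, analyse the first eligible case of each admission. Each death and each AKI then enters once.
3. Rerun Secondary Outcome 5 on all cases with a patient- or admission-level cluster term, as a sensitivity analysis.
4. Treat ending the laboratory windows at the next Anesthesia Start as a sensitivity analysis at most. It would shorten follow-up selectively in re-operated patients and could hide low nadirs and AKI. Step 2 removes duplicate rows but leaves second-operation values inside the first case's windows. That is acceptable if those values are described as part of the first case's postoperative course.

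The primary and transfusion-rate outcomes can keep all cases. The cost is a few sentences of protocol text and one de-duplication step. A few percent of cases leave Secondary Outcomes 3 and 5: about 2% to 5% if 2% to 5% of admissions have two eligible cases, and 9% if 10% do.

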### **Primary Outcome 1: The change in documented hemoglobin prior to an intraoperative transfusion.**

The hemoglobin of interest for this outcome is the pre-transfusion hemoglobin. See additional definitions above. Additionally, for this primary outcome we will perform a sensitivity analysis, following the same statistical methodology, to compare the effect of including only the first transfusion of the case in those cases with multiple transfusion with our definition.

First, the trend of median pre-transfusion hemoglobin measurement by quarter will be assessed for any change over time by testing whether the slope is significantly different from 0 using a bivariate linear regression model with the dependent variable of median pre-transfusion hemoglobin measurement. If the slope is not significantly different from 0, then the analyses for this aim will conclude. Otherwise, a Joinpoint analysis will be conducted to determine if there are any inflection points in the trend. If no inflection points are found and the slope is negative and significantly different from 0, then Hypothesis 1 will be assumed true. If the Joinpoint analysis finds one or more inflection points in the data, then a Student's t test or Mann-Whitney U test will be used to compare the values between consecutive quarters to analyze the significance of the change. A similar analysis will be conducted at the institution level.

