**Secondary Outcome 1: Proportion of cases receiving a packed red blood cell transfusion throughout the study period.**

An analysis similar to that for Primary Outcome 1 will be used to determine if there was a difference in trend over time for the proportion of cases receiving a pRBC transfusion. A similar analysis will be conducted at the institution level.

The proportion of people transfused at each hemoglobin threshold level (<6, 6-7, 7-8, 8-9, 9-10, >10) will be compared between 2012 and 2016 to determine if a change in practice occurred using a Chi-square or Fisher's Exact test, as appropriate.

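### Both primary hemoglobin trends pool all measurement methods and hematocrit/3 with no check by method, so a shift in the mix could pass for, or hide, a change in practice

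*Protocol*

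**What the plan says.** The measurement rule is in the protocol's Methods: "We will use intraoperative hemoglobin values documented, regardless of method of measurement". Measured hemoglobin takes priority only when both results exist at the same time ("We preferentially use hemoglobin measures over hematocrit if these are documented simultaneously"). For a hematocrit on its own, "we will perform an estimated conversion to hemoglobin, by dividing by 3".

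These pooled values feed both primary outcomes, defined as "the change in the pre-transfusion hemoglobin (ie transfusion threshold) and the nadir hemoglobin not-followed with an intraoperative transfusion over the course of the study period". Under Primary Outcome 1 the protocol sets the test, "testing whether the slope is significantly different from 0 using a bivariate linear regression model with the dependent variable of median pre-transfusion hemoglobin measurement", followed by a Joinpoint analysis if the slope is significant. It also sets the reading: "If no inflection points are found and the slope is negative and significantly different from 0, then Hypothesis 1 will be assumed true". Primary Outcome 2 is analyzed in the same way, and the trend is repeated by institution.

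The one sensitivity analysis stated for Primary Outcome 1 is to "compare the effect of including only the first transfusion of the case in those cases with multiple transfusion with our definition". The covariate lists in Methods, Statistical Analysis and Secondary Outcome 4 contain no indicator of method or of hematocrit conversion, and the primary trend test uses no covariates in any case. The planned site survey asks about point-of-care coagulation tests but not about how hemoglobin was measured.

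**The concern.** A constant difference between methods does no harm to a trend if the mix of methods is constant. If sites moved from hematocrit-only to measured hemoglobin, or from laboratory to bedside testing, during the 5.5 years, the quarterly median could move with no change in how patients were treated. A gradual move would look like a slope, and an abrupt one like an inflection. The direction is unknown, so the same mechanism could also hide a real fall.

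The selection rules may add to this. The nadir is the lowest value of the case, and with several transfusions the pre-transfusion value is the highest of those identified. Where one case holds values from two methods, the minimum tends to pick the lower-reading method and the maximum the higher-reading one.

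At stake is the main conclusion. Without inflections, a significant negative slope is taken as confirming the hypothesis, and the plan has no step that would show whether measurement contributed to it.

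**Working it through.** **Inputs from the protocol.** January 1, 2012 to July 1, 2017 is 5.5 × 4 = 22 quarters. Eight sites are anticipated. About 113,000 cases have an intraoperative hemoglobin or hematocrit. That last figure is a database count given without alpha, power, SD or effect size, so there is no calculation to reproduce.

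**Assumptions, none of them in the protocol.** Offset between methods 0.3 to 1.0 g/dL; shift in the share of one method 20 to 40 percentage points; equal site sizes; two-sided 0.05 for the slope test; SD 1.3 g/dL (pre-transfusion) and 1.8 g/dL (nadir); 3 to 10% of cases transfused; about 100,000 nadir cases; 32 to 35 g/dL for hemoglobin per unit of red-cell volume (MCHC).

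**1. Size of the artefact.** Spurious change in mean level = offset × change in share.
- Low: 0.3 × 0.20 = 0.06 g/dL. High: 1.0 × 0.40 = 0.40 g/dL.
- One of eight equal sites switching fully moves the share by 1/8 = 12.5 points: 0.3 × 0.125 = 0.04 g/dL to 1.0 × 0.125 = 0.125 g/dL.
- A 40-point shift needs 0.40 / 0.125 = 3.2 sites, so more than three switching in the same direction.

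**2. The hematocrit route alone.** At a true hemoglobin of 8.0 g/dL, hematocrit = 8.0 / MCHC × 100, and the plan then divides by 3.
- MCHC 32: 25.0 / 3 = 8.33, error +0.33. MCHC 33: 24.24 / 3 = 8.08, error +0.08.
- MCHC 34: 23.53 / 3 = 7.84, error −0.16. MCHC 35: 22.86 / 3 = 7.62, error −0.38.

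These errors are fixed offsets and give no slope while the converted share is constant. With a 20 to 40 point shift in that share, the absolute change runs from 0.08 × 0.20 = 0.02 to 0.38 × 0.40 = 0.15 g/dL.

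**3. Would the planned test pick it up?** I simulated the slope test on 22 quarterly medians. True hemoglobin was held constant, and a second method reading lower by the offset gained share linearly (400 runs per pre-transfusion row, 200 per nadir row). The Joinpoint step was not simulated.

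| Outcome (cases) | Offset, g/dL | Share of second method | Mean spurious change, g/dL | Trend declared |
|---|---|---|---|---|
| Nadir (100,000) | 0 | 20% to 60% | 0.00 | 5% |
| Nadir | −0.3 | 20% to 40% | −0.06 | 65% |
| Nadir | −0.5 | 20% to 40% | −0.10 | 99% |
| Nadir | −0.5 | 20% to 60% | −0.20 | 100% |
| Pre-transfusion (5,650) | 0 | 20% to 60% | 0.00 | 5% |
| Pre-transfusion | −0.3 | 20% to 40% | −0.06 | 10% |
| Pre-transfusion | −0.3 | 20% to 60% | −0.12 | 36% |
| Pre-transfusion | −0.5 | 20% to 60% | −0.20 | 77% |
| Pre-transfusion, one method only | −0.5 | 20% to 60% | 0.00 | 6% |

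For pre-transfusion hemoglobin at −0.5 and 20% to 60%, the rate is 52% with 3,390 transfused cases and 95% with 11,300. Extra between-quarter noise of 0.1 g/dL lowers the 77% to 48%. The nadir rows carry sampling noise only, so their rates are at the high end.

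**The case against.** Several points on the other side are good.

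- **No evidence of either condition.** The artefact needs both a systematic offset and a drifting mix. A reader might infer that the planned trends would be artefacts. The documents do not support that: they show neither condition, so the claim is only that the artefact could arise and that the plan could not detect it.
- **The displayed value may be the trigger.** If clinicians act on the number they see, the documented pre-transfusion value is the threshold, whatever device produced it. Pooling is then a defensible choice, and the pre-transfusion rows above, which shift the recorded value and leave behavior alone, overstate the risk. This stands for directly measured values. It does not cover hematocrit/3, where the clinician may never have seen a hemoglobin, or the nadir outcome.
- **The nadir is not a threshold.** It would be wrong to say that both outcomes misstate the transfusion threshold. For Primary Outcome 2 the artefact would be an apparent change in tolerated hemoglobin.
- **Partial safeguards exist.** The institution-level repeat would confine a switch at one site to that site's trend, and the preference for measured hemoglobin limits conversion. Neither tells a change of method within a site from a change of practice.
- **A wrong ratio is not a trend bias.** The error in dividing by 3 matters for the slope only if the converted share changes.
- **The hemoglobin bands are a separate matter.** Bands in Secondary Outcomes 1 and 5 share their edges at 7, 8 and 9, and some hematocrits divided by 3 land there. Measured values meet the same ambiguity, only secondary analyses are touched, and Secondary Outcome 5 allows the boundaries to be redefined. It adds nothing to this point.
- **A separate analysis plan may include such a check.** It may; none is shown. The protocol nonetheless fixes the pooling, the test and the reading of the slope, and names its sensitivity analysis.

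**Conclusion.** The point holds as a conditional one. The protocol fixes pooling across methods and reads a significant negative slope without inflection as a change in practice, with no step that separates measurement from practice. The plausible artefact is about 0.06 to 0.40 g/dL over the study, nearer 0.04 to 0.125 g/dL if one site in eight changed, and about 0.02 to 0.15 g/dL through hematocrit conversion alone. All three ranges rest on assumed offsets, shifts or MCHC values. The large nadir group gives no protection: in the simulation even a 0.06 g/dL artefact was declared a trend in 65% of runs. The weight of the concern lies on Primary Outcome 2 and on hematocrit-derived values in either outcome. It does not show that the design is invalid or that a trend, if found, would be spurious.

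**What to change.** Keep a flag on each value for directly measured or hematocrit-derived, which the analysts know because they make the conversion, and for laboratory or bedside source where it is coded. Report these shares by quarter and institution. Pre-specify a sensitivity analysis that repeats both primary trends without hematocrit-derived values and accounts for institution, for example by estimating the trend within site or at sites with a stable mix. Without that step, sites that moved to measured hemoglobin would enter the restricted set over time and create a new artefact of site composition.

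Interpret the primary trend alongside this analysis. Agreement supports a change in practice, and disagreement should be reported and discussed. The restricted result should not overrule the primary one, because it rests on a smaller and selected set.

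The cost is one or two flag variables, one table and one repeated analysis on data already extracted. The restricted analysis will have fewer cases, less precision and possibly a selected group of sites.
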